
Data Collection

Data will be collected by a number of different health professionals during enrollment, during the patient's postoperative hospital stay, by smart device application (app), and during the patient's routine postoperative follow up visits (1 month, 4 months, and 12 months). After surgery, no participants in any group will be subjected to any extra invasive tests or interventions related to their involvement in the study. Patients will not be informed whether or not they have received the study

drug until after all data collection is complete. The schedule of study activities and data collection are shown in Table 1.

1. **Pain assessment:** Postoperative pain will be assessed using the well-standardized and accepted visual analog pain scale. This data will be recorded at baseline, during the hospital stay, and at all follow-up visits. A smart device app will be used to record this information for the 7-day postoperative period. Questions will be asked morning, afternoon, and evening for every patient. Patients enter alarms for morning, afternoon, and evening the first time they use the app. Patients can later adjust these alarms if necessary. Timestamps will be recorded for each of these entries as patients will be asked about their 'average' pain over the preceding 4 hours, and they will be able to edit/modify prior entries at any time. Patients will also be asked during the first entry for the day if they were awoken from pain or nausea during the previous night, and if they click yes, they will be prompted to select pain scores corresponding to this event. There will be a comments section to provide patients the ability to enter text. Furthermore, during the hospital stay this data will be recorded with each vital sign assessment by the nursing per standard of care. The following scale will be used to assess pain:

[figure not shown]
©1983 Wong-Baker FACES® Foundation. www.WongBakerFACES.org
Used with permission.

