After the study is complete, statistical analysis will be performed using de-identified patient data to determine differences in primary and secondary outcomes. Repeated-measures analyses for VAS pain score (and change from baseline), knee ROM, functionality scores (SF-12 and KOOS, Jr.), and blood glucose will be done with a means model with SAS Proc Mixed (version 9, mixed linear models) providing separate estimates of the means by time on study (baseline, in hospital, day 7, and at 1,4 and 12 months after total knee arthroplasty) and treatment group (dexamethasone or control). A compound symmetry variance-covariance form among the repeated measurements will be assumed for each outcome and robust estimates of the standard errors of parameters will be used to perform statistical tests and construct 95% confidence intervals²⁶. T-tests will be used to compare the pairwise differences between the model-based treatment means (least-squares means) at each time point. Mean changes over time within a treatment group will be tested for linear trend. The model-based means are unbiased with unbalanced and missing data, so long as the missing data are non-informative (missing at random). A

dropout process is assumed to be missing at random if, conditional on the observed data, the dropout is independent of the unobserved measurements. Statistical tests will be two-sided. A p value < 0.05 will be considered statistically significant.

Adverse Event Reporting

At a six-month time point following initiation of the study, we will assess our results for any reportable adverse events, including postoperative infections. This data will be reported to the Emory Institutional Review Board (IRB). We will monitor for any adverse outcomes at each subsequent six-month interval.

Data Safety and Monitoring Plan

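### Compound symmetry from baseline to 12 months undercuts the plan's claim of unbiased means when dropout depends on earlier scores; late-visit means can shift, probably by a small amount

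*Combined protocol and SAP*

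**What the plan says.** The Statistical Analysis section of the combined protocol and SAP plans a repeated-measures mixed model for VAS pain, knee ROM, SF-12, KOOS, Jr. and blood glucose. Separate means are estimated by treatment group and "by time on study (baseline, in hospital, day 7, and at 1,4 and 12 months after total knee arthroplasty").

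- Covariance: "A compound symmetry variance-covariance form among the repeated measurements will be assumed for each outcome".
- Standard errors: "robust estimates of the standard errors of parameters will be used to perform statistical tests and construct 95% confidence intervals".
- Comparisons: "T-tests will be used to compare the pairwise differences between the model-based treatment means (least-squares means) at each time point".
- Missing data: "The model-based means are unbiased with unbalanced and missing data, so long as the missing data are non-informative (missing at random"). The definition follows: a "dropout process is assumed to be missing at random if, conditional on the observed data, the dropout is independent of the unobserved measurements".

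The section names no alternative covariance structure, no check of the assumed one and no sensitivity analysis for missing data. The documents state no SD, no within-patient correlation and no expected dropout rate.

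**The concern.** Under missing at random, a likelihood-based mean at a late visit borrows from the earlier scores of patients who have left. The covariance model fixes how much is borrowed. If it is wrong, the borrowing is wrong and the estimated mean moves. The plan's statement names the missing-data condition and omits the covariance condition.

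Compound symmetry imposes one variance and one correlation on all visits, so pain in hospital predicts pain at 12 months exactly as well as it predicts pain at day 7. That is hard to believe for scores taken before surgery, in the acute phase and a year later, by nurses, by app and in clinic.

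Some missing data are foreseeable. Follow-up runs through the "routine postoperative follow up visits (1 month, 4 months, and 12 months"), day-7 pain relies on patients' own app entries, and the Consent Process section allows withdrawal at any time. The background section presents long-term knee function as a distinguishing aim, and the plan tests arm differences at every time point, so the late means will be read as results.

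**Working it through.** **Stated figure.** The plan gives 47 per arm for 90% power at a 1.5-point difference. Without an SD this cannot be reproduced, only back-solved. From n = 2(1.96 + 1.2816)² SD² / 1.5², with n = 47 and a two-sided 5% level, SD = 1.5 × √(47 / (2 × 10.51)) = 2.24. This is used below as an assumption.

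**Scale.** The standard error of a pairwise difference is 2.24 × √(2/47) = 0.46 with complete data. With 20% lost (37.6 per arm) it is 2.24 × √(2/37.6) = 0.52.

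**Mechanism.** Suppose only the 12-month value is missing. Let δ_j be the amount by which completers' expected score at visit j lies below that of the whole arm. The compound-symmetry estimate at 12 months is the completers' 12-month mean plus b times the sum of the five earlier δ_j, with b = ρ / (1 + 4ρ). Hence

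bias = b × (δ₁ + … + δ₅) − δ₁₂ₘ.

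A correct covariance would give each earlier visit its own weight, and the terms would cancel. If dropout is completely at random, every δ is zero and so is the bias.

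**Hand calculation (all inputs assumed).**
1. The correlation between visits is 0.8 × exp(−days apart / 90), and SD is 2.24. Visits fall 14 days before surgery and on days 1, 7, 30, 120 and 365.
2. The log-odds of missing the 12-month visit are −1.6 + z, where z is the standardised average of the hospital and day-7 scores. Numerical integration gives 20.7% loss and a completers' mean z of −0.179.
3. δ_j = 2.24 × 0.179 × (correlation of visit j with z). For the hospital visit the correlation is (1 + 0.748) / √(2 × 1.748) = 0.935, so δ = 0.375.
4. The five earlier values are 0.281, 0.375, 0.375, 0.257 and 0.095, which sum to 1.383. At 12 months δ is 0.006.
5. The fitted common correlation is ρ = 0.353, so b = 0.353 / 2.412 = 0.146.
6. Bias = 0.146 × 1.383 − 0.006 = +0.20 points.

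With a 30-day decay in place of 90 days, ρ = 0.183, b = 0.183 / 1.732 = 0.106 and the sum is 1.081, so the bias is +0.11.

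**Large-sample simulation.** Pain at the plan's six times, SD 2.24, about 20% dropout, 300,000 to 1,000,000 patients per arm. The same data were fitted with compound symmetry and with an unstructured covariance.

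| Assumed truth | Shift under compound symmetry, 12 months |
|---|---|
| Constant correlation 0.5, dropout depends on scores | about 0 |
| Any correlation pattern, dropout completely at random | about 0 |
| Correlation decays with days, dropout driven by hospital and day-7 pain: arm mean | +0.10 to +0.20 |
| Same, arm difference, same dropout rule, no early effect | about 0 |
| Same, arm difference, same rule, 1.5-point early effect | 0.04 to 0.07 |
| Same, arm difference, dropout depends on pain in one arm only | 0.10 to 0.20 |
| Same, arm difference, dependence opposite in the two arms | 0.21 to 0.40 |
| AR(1) by visit (0.5 to 0.8), dropout driven by last score: arm mean | at most about 0.03 (up to about 0.08 at 1 month) |

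Unstructured covariance gave about 0, within about 0.01, throughout.

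A further large-sample check with about 20 to 30% of placebo missing at 12 months gave a placebo-mean shift of +0.03 to +0.20 and an arm-difference shift of +0.02 to +0.09. Unstructured stayed within about 0.03 at every visit. With heavier, unequal loss (35% placebo, 20% high dose) and decay by days, the shifts reached +0.28 and +0.14.

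**Effect on a test.** A shift of 0.02 to 0.1 is 0.02/0.5 = 0.04 to 0.1/0.5 = 0.2 standard errors. At 0.2, a nominal 5% two-sided test rejects with probability Φ(−1.76) + Φ(−2.16) = 0.039 + 0.015, about 5.5%.

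**The case against.** The plan's statement is conditional, it concerns model-based means, and the compound-symmetry assumption is disclosed just before it. Robust standard errors are a recognised guard against a wrong covariance. Every size quoted above rests on inputs that the documents do not supply, and the results vary: AR(1) by visit with last-score dropout gave at most about 0.03 at 12 months in one set of runs, while another assumed set (correlation 0.6 per visit, SD 1.6 to 2.2, about 25% of placebo missing) gave +0.13. The effect on contrasts is a fraction of a standard error. The in-hospital pain comparisons should lose few data, and analgesic use, the other primary outcome, is not among the outcomes listed for this model.

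Most of this stands and limits the size of the point. It does not supply the missing condition: robust standard errors leave the point estimates where they are. Nor does a dropout rule common to all arms cancel fully, because an early analgesic effect makes dropout unequal.

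A reader might infer more than the documents support:
- That falling correlations alone break the claim. They do not; dropout must also depend on observed scores.
- That day-7 contrasts are materially distorted. With 15% of placebo already missing at day 7, the placebo mean there moved by only −0.03 to −0.07, and by about 0 when dropout began later.
- That ROM and function contrasts have been shown to be shifted. Size was checked for pain only. In Table 1, ROM shares the span from hospital to 12 months, KOOS, Jr. and SF-12 have four time points with none in hospital or at day 7, and glucose has no visit after discharge.

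**Conclusion.** The point holds as an omitted condition. Unbiased late-visit means need missing at random and an adequate covariance model, and the plan fixes a covariance that is implausible over this time span. Bias arises only if variances or correlations change over time and dropout also depends on observed scores. With about 20 to 30% of placebo missing at 12 months, a fair range is 0.03 to 0.2 VAS points in an arm mean and 0.02 to 0.1 in an arm difference. Larger shifts need heavier loss or a dropout mechanism that differs between arms, and nothing in the documents indicates either. The range depends on the assumed SD, correlations and dropout rule. It is small against a standard error of about 0.5 and the 1.5-point target. This is a correction worth making because it is cheap; it does not threaten the trial's main early comparison.

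**What to change.** In the Statistical Analysis section:
1. Replace compound symmetry with an unstructured covariance and small-sample degrees of freedom.
2. State how the inpatient measurements are reduced to one in-hospital value per patient. If each inpatient day entered separately, the matrix would grow and become sparse after discharge.
3. Name heterogeneous Toeplitz as the fallback if the unstructured model does not converge, and keep robust standard errors if the fallback is used.
4. Reword the missing-data statement to say that unbiasedness requires both missing at random and an adequate covariance model.

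The cost is a few lines of text and code, and more covariance parameters: k(k + 1)/2, which is 21 for the six pain times and 10 for the four questionnaire times. The planned 141 patients should support this, with a possible need for the fallback. Sample size and data collection are unchanged.

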Our objective is to determine the effect of and compare two different doses of IV dexamethasone given preoperatively before TKA, when compared to placebo, using the outcome measures listed below:

Primary Outcome Measures

- To assess patient reported visual analog pain scores.
- To assess patient controlled analgesic usage.

Secondary Outcome Measures

1. To assess the soft tissue swelling about the operative knee after steroid administration.
2. To assess postoperative glucose levels after steroid administration.
3. To assess rehabilitation parameters such as postoperative knee range of motion and time to physical therapy clearance.
4. To assess incidence of nausea and vomiting postoperatively after steroid administration.
5. To assess patient satisfaction and function scores at 4 months with both Short Form (SF) – 12 and Knee Injury and Osteoarthritis Outcome Score Short Form (KOOS, Jr.) scores.
6. To assess hospital admission characteristics such as length of stay and rate of readmission.
7. To assess the risk of infection at 4 months and wound drainage at 7 days after perioperative steroid administration in total knee arthroplasty.

Study Design and Methods

We plan to conduct a prospective, double-blinded, randomized, placebo-controlled trial to evaluate perioperative glucocorticoid administration in total knee arthroplasty. There will be three arms in the study: 1) Placebo, 2) 10 mg dexamethasone, and 3) 20 mg dexamethasone.

Consent to Participation in the Study

Patients will be given the opportunity to participate in the study at the time of consent for surgery and blood product, which typically takes place in clinic during an evaluation for severe end-stage arthritis. It will be emphasized that study participation is optional, and that patients may be randomized to the control or placebo group. Patients will sign the combined informed consent and HIPAA form in order to participate in the study.

Method of Randomization

Once a patient chooses to be part of the study, he/she will be randomized in a blocked fashion to either the control group or to one of two intervention groups. Randomization will occur after informed consent has been obtained from the patients and after the preoperative screening examination is complete. Patients and investigators will be blinded to the randomization assignment. Emory's Investigational Drug Services will randomize each patient prior to dispensing the blinded dexamethasone/placebo doses.

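### VAS pain is compared between all pairs of arms at five postoperative times, each at 0.05, with no primary time: about a 9–21% chance of a false claim of benefit over placebo (between-time correlation assumed 0.9 to 0)

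*Combined protocol and SAP*

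**What the plan says.** Under Primary Outcome Measures the protocol lists VAS pain, with no time attached, and a second item, "To assess patient controlled analgesic usage". Statistical Analysis sizes the trial on pain: 47 patients per arm for 90% power, with a difference of 1.5 between placebo and low dose, 1.5 between low and high dose, and so 3 between placebo and high dose.

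The same section fits a repeated-measures model with means at "baseline, in hospital, day 7, and at 1,4 and 12 months after total knee arthroplasty", and then: "T-tests will be used to compare the pairwise differences between the model-based treatment means (least-squares means) at each time point". Tests are two-sided, and "A p value < 0.05 will be considered statistically significant". The model assumes compound symmetry, but "robust estimates of the standard errors of parameters will be used to perform statistical tests".

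On the arms, Study Design and Methods states: "There will be three arms in the study: 1) Placebo, 2) 10 mg dexamethasone, and 3) 20 mg dexamethasone". The Objectives aim to "compare two different doses of IV dexamethasone" as well as to compare with placebo. The model sentence, however, describes "treatment group (dexamethasone or control"), which names only two levels.

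Data Collection (item 1, pain assessment) has pain recorded at every nursing vital-sign check in hospital, and three times a day by app for seven days. No rule reduces the hospital readings to the single in-hospital value in the model.

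No section names a primary time, a primary contrast, an overall test, a testing order or a multiplicity adjustment.

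**The concern.** As written, a claim that dexamethasone reduces pain can rest on any of ten dose-versus-placebo tests, each read at 0.05. The time and dose to headline can be chosen once the results are known. The undefined in-hospital summary adds a further free choice. The repeated-measures model accounts for correlation between times but does not adjust the pairwise tests that follow from it.

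At stake is how the main result can be read. The protocol's background says the best dose is not known, so the trial is meant to inform dose choice. A positive pain finding at one time for one dose would carry much weaker evidence than its p-value suggests.

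**Working it through.** **1. The plan's own figure.** For two means, n per arm = 2·SD²·(z₀.₉₇₅ + z₀.₉₀)² / δ². With n = 47, δ = 1.5 and z-sum 1.960 + 1.282 = 3.242, SD = 1.5 / (3.242 × √(2/47)) = 2.24. The t-test version gives 2.22. The protocol states no SD, test or sizing alpha, so other routes to 47 are possible:

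- pairwise t-test at 0.05/3: SD about 1.95;
- three-arm overall F test on means 0/1.5/3: noncentrality 47 × (1.5² + 0² + 1.5²) / SD² = 211.5 / SD², and 90% power gives SD about 4.04.

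The figure of 47 is therefore neither confirmed nor contradicted. The SD does not affect the error rates in steps 3 and 4, which are computed under no effect. It matters only for the power cost of the fix.

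**2. Count of tests.** Three arms give 3 pairs. Five post-surgery times (in hospital, day 7, months 1, 4 and 12) give 3 × 5 = 15 tests, of which 2 × 5 = 10 are against placebo. If all 15 were independent, the chance of at least one false positive would be 1 − 0.95¹⁵ = 53.7%. That overstates it, because pairs share arms and times share patients.

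**3. Simulation under no effect.** Inputs: 47 per arm, complete data, two-sided 0.05, 141 − 3 = 138 df, and the plan's compound symmetry. The between-time correlation is assumed.

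| Correlation | Any of 15 significant | Same, robust SE | Some dose better than placebo at some time |
|---|---|---|---|
| 0 | 48% | 50% | 21% |
| 0.2 | 46% | 48% | 19% |
| 0.5 | 40% | 42% | 16% |
| 0.7 | 32% | 34% | 13% |
| 0.9 | 23% | 25% | 9% |

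With robust standard errors, the last column runs from 22% to 10%. The comparator for that column is 2.5%, the chance that one two-sided 0.05 test falsely favours the drug. As the correlation nears 1, the five times act as one. Three unadjusted pairs then give about 12% for any significant result and 4.5% for a false claim of benefit.

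**4. Pooled reading.** If the two dexamethasone arms are combined, there are five tests. The chance of any significant result is 23% to 10%, and of a false claim of benefit 12% to 5%, at correlation 0 to 0.9.

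**5. Check of the proposed rule.** At one time, with the 2-df overall test at 0.05 followed by the three pairwise tests at 0.05, the error is 5.0% when all arms are equal and 5.0–5.1% when one arm is shifted. The second result is expected, since only one true null pair then remains. With the planned robust standard errors, the error under no effect is about 5.5–5.7%. A false claim of benefit occurs about 2.1% of the time (2.3% robust). A Tukey adjustment at one time also gives 5.0%.

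**The case against.** The strongest case against has five parts.

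- **No family-wise rate is promised.** The plan sets 0.05 per test and frames its outcomes as things to assess. A reader might infer that it claims 5% overall and fails to deliver it. The documents do not support that, because no such claim is made. What stands is that pain is called primary and sizes the trial, yet nothing bounds the error or the selection.
- **The 23–48% figure is not the chance of a false claim of benefit**, though a reader might take it so. It also counts dose-versus-dose results and results where dexamethasone looks worse. The figure that bears on the trial's claim is 9–21%.
- **Zero correlation is a bound.** Pain scores from the same patient are unlikely to be uncorrelated, and a repeated-measures model presupposes that they are correlated. The 21% and 48% ends should not be read as likely values.
- **The model sentence may mean two groups.** That reading lowers the figures. It conflicts with the three arms, the aim of comparing doses, the sizing on both dose contrasts and the word pairwise. The text should still be corrected, since it permits the reading.
- **All times may be reported**, so readers could judge the pattern for themselves. That helps, but it does not say which result is confirmatory.

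The count of 15 is not inflated. It leaves out the baseline comparison, the second primary outcome and the change-from-baseline analysis. Raw and change scores together would give about 53–61% for any significant result.

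**Conclusion.** The concern holds. Under the three-arm reading and no drug effect, the plan allows a false claim that a dose reduces pain versus placebo about 9–21% of the time, against 2.5% for one such test. Any significant result among the 15 occurs 23–48% of the time. Under the pooled reading the figures are 5–12% and 10–23%. These rest on an assumed correlation of 0.9 to 0, complete data, 47 per arm and five post-surgery times. At every correlation from 0 to 0.9, and under both readings, the rate is above that of a single test.

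Two stronger conclusions are not supported. The sample size is not shown to be wrong, because the missing SD means it cannot be checked. Nor is the remedy free of power cost under every plausible SD. This is best treated as a cheap improvement: a gap in the rules for the primary claim that plan text alone can close.

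**What to change.** Change the Statistical Analysis section as follows.

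- Name one primary VAS time window in the early postoperative period, with a rule for combining the readings in it.
- In that window, test the three arms with the 2-df overall test at 0.05. Run the three pairwise tests at 0.05 only if it is significant. A Tukey adjustment would also serve.
- Replace the two-level description of treatment group with the three arms.
- Report the other times as secondary, with 95% confidence intervals.
- If analgesic use stays co-primary, split alpha 0.025/0.025 and apply the same two steps to each outcome.

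**Cost.** No new data or patients are needed, and the later times lose confirmatory status. The power cost has to be given as a range, because the SD is not stated. The table shows power for placebo versus high dose at 47 per arm, without and then with the overall-test step. Means are pain reductions for placebo/low/high dose, and the SDs are the three back-solved values.

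| Means | SD 1.95 | SD 2.22 | SD 4.04 |
|---|---|---|---|
| 0/1.5/3 (the protocol's) | no loss | no loss | 95% to 90% |
| 0/1.5/1.5 | 96% to 95% | 90% to 88% | 43% to 35% |
| 0/0.75/1.5 | 96% to 92% | 90% to 83% | 43% to 31% |

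With both the overall-test step and the alpha split, power at SD 1.95, 2.22 and 4.04 is 91%, 81% and 25% for means 0/1.5/1.5. For means 0/0.75/1.5 it is 86–87%, 75% and 22%. The split is needed only if there are two primary outcomes. Stating the SD and the sizing method would show which column applies.
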